### 8.1.2. Vital Signs

- Vital signs will be measured in a semi-supine position after 5 minutes rest and will include temperature, systolic and diastolic blood pressure, and pulse.

### 8.1.3. Electrocardiograms

- Triplicate 12-lead ECG will be obtained as outlined in the SoA (see Section 1.3) using an ECG machine that automatically calculates the heart rate and measures PR, QRS, QT, and QTc intervals. Refer to Section 7 for QTc withdrawal criteria and additional QTc readings that may be necessary.
- At each time point at which triplicate ECGs are required, 3 individual ECG tracings should be obtained as closely as possible in succession, but no more than 2 minutes apart. The full set of triplicates should be completed in less than 4 minutes. 12-lead ECGs will be performed with the subject in a supine position having rested in this position for at least 5 minutes beforehand.

### 8.1.4. Clinical Safety Laboratory Assessments

- Refer to [Appendix 2](#) for the list of clinical laboratory tests to be performed and to the SoA for the timing and frequency.
- The investigator must review the laboratory report, document this review, and record any clinically relevant changes occurring during the study in the AE section of the CRF. The laboratory reports must be filed with the source documents. Clinically significant abnormal laboratory findings are those which are not associated with the underlying disease, unless judged by the investigator to be more severe than expected for the participant's condition.
- All laboratory tests with values considered clinically significantly abnormal during participation in the study or within 7 days after the last dose of study intervention should be repeated until the values return to normal or baseline or are no longer considered significantly abnormal by the investigator or medical monitor.
- If such values do not return to normal/baseline within a period of time judged reasonable by the investigator, the etiology should be identified, and the sponsor notified.
- All protocol-required laboratory assessments, as defined in [Appendix 2](#), must be conducted in accordance with the laboratory manual and the SoA.
  - **Screening for SARS-CoV-2:** Study participants will be monitored at Screening and daily while inpatients for COVID-19 symptoms. Investigator(s) should utilise the World Health Organisation (WHO) Case Definitions to classify COVID-19 cases [[World Health Organisation](#), 2020]. While outpatients, participants should report to the unit any symptoms suggestive of COVID-19. All participants who experience symptoms suggestive of COVID-19 should be

isolated in the unit or at home and tested for SARS-CoV-2 using an approved molecular test (PCR or antigen test). If a participant tests positive or becomes symptomatic with suspected/confirmed COVID-19 while on-unit, then the remaining participants in that cohort on the unit should be discharged). The investigator should consider any participant testing positive for SARS-CoV-2 being discontinued from study drug if COVID-19 symptoms are moderate to severe. Appropriate contact tracing for all participants testing positive will be performed within the unit. This should be done in accordance with local legislation and guidelines. Appropriate follow up should be implemented for participants who discontinue the study due to COVID-19.

### **8.1.5. Suicidal Ideation and Behavior Risk Monitoring**

- Participants will be monitored appropriately and observed closely for suicidal ideation and behavior or any other unusual changes in behavior. It is recommended that the investigator consider mental health consultation or referral for participants who experience signs of suicidal ideation or behavior. Participants presenting with new onset/treatment emergent depression should be advised to contact the investigator immediately if symptoms of severe acute depression (including suicidal ideation/attempts) develop, because medical intervention and discontinuation of the study medication may be required.

## **8.2. Adverse Events and Serious Adverse Events**

The definitions of an AE or SAE can be found in [Appendix 3](#).

AEs will be reported by the participant (or, when appropriate, by a caregiver, surrogate, or the participant's legally authorized representative).

The investigator and any qualified designees are responsible for detecting, documenting, and reporting events that meet the definition of an AE or SAE and remain responsible for following up AEs that are serious, considered related to the study intervention or the study, or that caused the participant to discontinue the study (see Section [7](#)).

### **8.2.1. Time Period and Frequency for Collecting AE and SAE Information**

- All SAEs will be collected from the start of intervention until the follow-up Week 52 visit at the time points specified in the SoA (Section [1.3](#)). However, any SAEs assessed as related to study participation (e.g., study intervention, protocol-mandated procedures, invasive tests, or change in existing therapy) or related to a GSK/ViiV product will be recorded from the time a participant consents to participate in the study.
- All AEs will be collected from the start of intervention until the follow-up Week 52 visit at the time points specified in the SoA (Section [1.3](#)).

- Medical occurrences that begin before the start of study intervention but after obtaining informed consent will be recorded on the Medical History/Current Medical Conditions section of the CRF not the AE section.
- All SAEs will be recorded and reported to the sponsor or designee immediately and under no circumstance should this exceed 24 hours, as indicated in [Appendix 3](#). The investigator will submit any updated SAE data to the sponsor within 24 hours of it being available.
- Investigators are not obligated to actively seek AEs or SAEs after the conclusion of the study participation. However, if the investigator learns of any SAE, including a death, at any time after a participant has been discharged from the study, and he/she considers the event to be reasonably related to the study intervention or study participation, the investigator must promptly notify the sponsor.

#### **8.2.2. Method of Detecting AEs and SAEs**

- The method of recording, evaluating, and assessing causality of AEs and SAEs and the procedures for completing and transmitting SAE reports are provided in [Appendix 3](#).
- Care will be taken not to introduce bias when detecting AE and/or SAE. Open-ended and non-leading verbal questioning of the participant is the preferred method to inquire about AE occurrence.

#### **8.2.3. Follow-up of AEs and SAEs**

- After the initial AE/SAE report, the investigator is required to proactively follow each participant at subsequent visits/contacts. All SAEs, will be followed until the event is resolved, stabilized, otherwise explained, or the participant is lost to follow-up (as defined in Section [7.3](#)). Further information on follow-up procedures is given in [Appendix 3](#).

#### **8.2.4. Regulatory Reporting Requirements for SAEs**

- Prompt notification by the investigator to the sponsor of a SAE is essential so that legal obligations and ethical responsibilities towards the safety of participants and the safety of a study intervention under clinical investigation are met.
- The sponsor has a legal responsibility to notify both the local regulatory authority and other regulatory agencies about the safety of a study intervention under clinical investigation. The sponsor will comply with country-specific regulatory requirements relating to safety reporting to the regulatory authority, Institutional Review Boards (IRB)/Independent Ethics Committees (IEC), and investigators.
- For all studies except those utilizing medical devices investigator safety reports must be prepared for suspected unexpected serious adverse reactions (SUSAR) according to local regulatory requirements and sponsor policy and forwarded to investigators as necessary.

- An investigator who receives an investigator safety report describing a SAE or other specific safety information e.g., summary or listing of SAEs) from the sponsor will review and then file it along with the Investigator's Brochure and will notify the IRB/IEC, if appropriate according to local requirements.

### **8.2.5. Pregnancy**

- Details of all pregnancies in female participants and female partners of male participants will be collected after the start of study intervention and until 52-week post injections.
- If a pregnancy is reported, the investigator should inform GSK/ViiV within 24 hours of learning of the pregnancy and should follow the procedures outlined in [Appendix 4](#).
- Abnormal pregnancy outcomes (e.g., spontaneous abortion, fetal death, stillbirth, congenital anomalies, ectopic pregnancy) are considered SAE.

### **8.3. Treatment of Overdose**

For the oral lead in phase of this study, any dose of CAB > 30 mg and/or RPV > 25mg within a 24-hour time period will be considered an overdose.

For the injection phase of the study, any dose of CAB LA > 600 mg and/or RPV LA > 900 mg will be considered an overdose.

GSK/ViiV does not recommend specific treatment other than supportive care for an overdose.

The investigator will use clinical judgement to treat any overdose.

In the event of an overdose, the investigator should:

1. Contact the Medical Monitor immediately.
2. Closely monitor the participant for AE/SAE and laboratory abnormalities until CAB and/or RPV can no longer be detected systemically.
3. Document the quantity of the excess dose as well as the duration of the overdosing in the CRF.

Decisions regarding dose interruptions or modifications will be made by the investigator in consultation with the Medical Monitor based on the clinical evaluation of the participant.

### **8.4. Pharmacokinetics**

Blood samples of CAB (~ 2 mL each) and RPV (~ 2mL each) will be collected for measurement of plasma concentrations of CAB and RPV, respectively, as specified in the SoA.

- Samples may be collected at additional time points during the study if warranted and agreed upon between the investigator and the sponsor. The timing of sampling may be altered during the course of the study based on newly available data (e.g.,

to obtain data closer to the time of peak plasma concentrations) to ensure appropriate monitoring.

- Instructions for the collection and handling of biological samples will be provided by the sponsor. The actual date and time (24-hour clock time) of each sample will be recorded.
- Samples will be used to evaluate the PK of CAB and RPV. Genetic analyses will not be performed on these plasma samples.

Plasma analysis for CAB concentration determination will be performed under the control of GlaxoSmithKline, the details of which will be included in the Study Reference Manual (SRM). Concentrations of CAB will be determined in plasma samples using the currently approved bioanalytical methodology. Raw data will be archived at the bioanalytical site (detailed in the SRM).

Plasma RPV analysis will be performed under the control of Janssen R&D. Concentrations of RPV will be determined in plasma samples using the currently approved bioanalytical methodology. Raw data will be archived at the bioanalytical site.

**Permitted sampling window for the OLI Phase:**

Plasma PK Assessment	Permitted Sampling Window
Day 1 (1 h)	±15min
Day 1 (2 h)	±15min
Day 1 (3 h)	±30 min
Day 1 (4 h)	±15min
Day 1 (6 h)	±30 min
Day 1 (8 h)	±1h
Day 1 (12 h)	±1h
Day 2 (24 h)	±2h
Day 14	±1 day
Day 29	22-26h from Day 28 dose

Permitted sampling window for injection phase is provided in SoA.

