#### 1.3.1. Screening and Oral Lead-in Phase

Study Period	Screening 	Oral Lead-in 			Day 29	Early Withdrawal 	Washout Period
		Dosing Days 1-28					
Visit Window	Within 30 days of oral lead-in	Day -1	Day 1	Day 2	Day 14	Within 24 hours of the Day 28 last dose	EW
Informed Consent	X						10 – 14 days
Demographics	X						
Medical / Medication / Drug / Alcohol History	X						
Inclusion/Exclusion Criteria 	X	X					
Height, Weight, BMI	X						
Physical Exam	X	X					
Vital Signs 	X	X	X	X	X	X	
12-Lead ECG	X	X			X		
Drug / Alcohol Screen 	X	X					

Study Period	Screening 		Oral Lead-in 			Day 29	Early Withdrawal 	Washout Period
			Dosing Days 1-28					
Visit Window	Within 30 days of oral lead-in	Day -1	Day 1	Day 2	Day 14	Within 24 hours of the Day 28 last dose	EW	10 – 14 days
Pregnancy Test 	X		X		X	X		
Testing for SARS-CoV-2 	X	X						
Hepatitis B, Hepatitis C Screening	X							
HIV Test	X							
Urine Dipstick	X							
Hematology with differential; Clinical Chemistry Tests 	X		X	X	X	X	X	
Coagulation Tests	X							
Admit to clinic		X						
Dispense Oral lead-in IP			X					
Administer oral CAB + RPV 			X	X	X			
Dispense Medication Dosing Diary				X				
Drug accountability/ pill count/review drug diary				X	X	X		
Blood plasma PK sampling 			X	X	X	X	X	
AE Assessment 			X	X	X	X	X	
Concomitant Medication Review			X	X	X	X	X	
Genetic sample 			X					
Discharge from the clinic				X				

1. Screening may occur over more than one visit but within 30 days of the first dose of oral CAB and RPV in the oral lead in phase.

2. Eligibility criteria must be carefully assessed at the Screening visit and confirmed at the Day 1 Oral lead-in phase visit and re-confirmed prior to injection.
3. Prior to administering the first oral dose of CAB and RPV, study personnel must verify the following pre-dose assessments to be within normal limits prior to administration: vital signs, pregnancy test (negative; Females of Reproductive Potential (FRP) only. The results of the Drug/Alcohol screen, hematology with differential, and clinical chemistry tests on Day 1 are not required prior to administering the first oral doses of CAB and RPV but should be drawn prior to CAB and RPV administration.

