4. Two consecutive approved molecular tests (PCR or antigen test) must be conducted on all study participants and separated by >48 hours. Following the second test for SARS-CoV-2, participants should be quarantined within the unit. Once the second test is negative, the participant can be released into the unit and follow Infection Control practices
5. Oral CAB and RPV dosing Days 1 to 28. Day 1, Day 2, and Day 14 doses should be administered in the clinic.
6. PK sampling – On Day 1 - 1h, 2h, 3h, 4h, 6h, 8h, and 12h, and Day 2 PK between 22 to 26 h post first oral dose. On Day 14 pre-dose samples. Day 29 PK should occur between 22 to 26 hours from the last dose on Day 28. Total of 20 PK samples (10 for CAB, 10 for RPV assay) will be collected during oral lead-in phase. Please refer to Section 8.4 for permitted PK window for OLI phase.
7. AE assessment will include a brief, symptom-directed physical exam as needed.
8. Genetic sample - collect the sample at the earliest convenient time after the first dose in the oral lead in phase on Day 1.
9. If a participant is withdrawn prior to receiving the CAB LA and/or RPV LA injection, a follow-up/withdrawal visit should be scheduled 10-14 days after the last oral dose of CAB and RPV.

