#### **4.1.2. Oral Lead-in Phase**

Participants that are eligible to participate will be admitted to the clinic on Day 1 of the OLI phase and receive their first oral dose of CAB 30 mg and RPV 25 mg with a standard breakfast after the completion of all pre-dose assessments. Participants will undergo sparse PK sampling of blood as described in Schedule of Activities (SoA). After a pre-dose 24-hour PK sample collection and laboratory assessments, participants will take their Day 2 study interventions with a meal at the clinic. Participants will be dispensed a sufficient supply of oral CAB + RPV tablets to complete 26 days of once daily dosing at home (with exception of the visit days at the clinic) and be counseled to take their dose with a meal at about the same time each day, before getting discharged on Day 2.

On Day 14 of the OLI phase, the participants will return to the clinic. A pre-dose PK sample will be collected. In addition, this visit will include assessment of safety, tolerability, and participant adherence to study drug. Participants should bring their supply of oral CAB + RPV to the Day 14 visit to have drug accountability performed. Participants will receive Day 14 dose at the clinic.

Participants will return to the clinic on Day 29, within 24 hours of last dose on Day 28 for PK, drug accountability, and all assessments performed as described in the SoA Section 1.3. The participants will begin a wash-out period of 10-14 days, during which no CAB and RPV will be administered.

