### **10.2. Sample Size Determination**

There was no formal calculation of power or sample size for this study. Approximately 15 participants will receive CAB LA + RPV LA IM injections and provide informative safety and pharmacokinetic data based on feasibility considerations.

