### **8.3. Statistical Analyses**

All the derived pharmacokinetic parameters will be summarized and listed for the PP population by study phase and treatment. For each of these PK parameters, with the exception of  $t_{max}$ , the following descriptive summary statistics will be calculated for each treatment: n, arithmetic mean with associated 95% CI, standard deviation, median, minimum, maximum, geometric mean with associated 95% CI, standard deviation of logarithmically transformed data, and the geometric coefficient of variation ( $CV_b(\%)$ ). For  $t_{max}$ , the n, median, minimum, and maximum summary statistics will be provided.

Data display specifications for derived PK parameter summaries and listings are given in [Appendix 9](#) of this RAP

PK samples collected outside the protocol defined time-windows and/or other protocol deviations will be reviewed by the study team to determine whether the sample will be excluded from PK analyses. PK reporting will also consider planned Quality Tolerance Limit (QTL) outcomes affecting study data quality. Details are found in the QTL Report.

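### The pre-dose Day 14 oral lead-in sample has a visit-day window but no limit on hours since the previous dose, and Day 29 PK timing is stated in two ways that agree only at 22-24 h

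*Protocol*

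**What the plan says.** **Day 14.** Footnote 6 of the protocol schedule (section 1.3.1) specifies "On Day 14 pre-dose samples", and section 4.1.2 agrees. The window table in section 8.4 gives this sample ±1 day and nothing else. In the same table the Day 2 (24 h) sample has ±2 h and the Day 29 sample has "22-26h from Day 28 dose".

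**Day 29.** Two rules appear:
- Section 4.1.2: "Participants will return to the clinic on Day 29, within 24 hours of last dose on Day 28 for PK". The visit-window row of the schedule has "Within 24 hours of the Day 28 last dose", and the SAP schedule (section 11.1.1) repeats that row.
- Footnote 6 of the protocol schedule: "Day 29 PK should occur between 22 to 26 hours from the last dose on Day 28". This matches section 8.4, to which the footnote refers the reader. Footnote 6 of the SAP schedule also gives 22-26 h, for the Day 29 assessments generally.

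**Use in the analysis.** SAP Table 7 derives the lead-in trough, Cτ, from Day 29. SAP 8.1 summarises concentrations by nominal time. SAP Table 8 slots PK samples by calendar day (13-15 and 28-30). SAP 8.3 states that "PK samples collected outside the protocol defined time-windows and/or other protocol deviations will be reviewed by the study team", to decide on exclusion.

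**The concern.** A pre-dose sample under once-daily dosing is a trough only if it falls about 24 h after the previous dose. For Day 14 the documents fix the calendar day and the pre-dose status but not that gap. The previous dose is normally taken at home, and participants are asked only to take it with a meal at a roughly constant time of day, which need not match the clinic appointment. A mistimed Day 14 sample therefore meets every stated window and triggers no review on timing.

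For Day 29 the difficulty is different: whether a given sample is a deviation depends on which section is read. That sample supplies Cτ, and SAP 8.3 relies on the protocol window to decide what to review.

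Recording actual times does not remove either problem. Non-compartmental analysis uses actual times, but the concentration summaries use nominal times, and Cτ is simply the Day 29 concentration with no adjustment for when it was drawn.

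**Working it through.** **1. Completeness of the window table.** Section 8.4 has seven Day 1 rows plus Day 2, Day 14 and Day 29: 7 + 3 = 10 samples. For two analytes, 10 × 2 = 20, which reproduces the total in footnote 6. The table covers every lead-in PK sample, and Day 14 is the only one whose window is in days.

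**2. Day 29 rules as intervals (hours after the Day 28 dose).**
- Section 8.4 and footnote 6: 22 to 26.
- Section 4.1.2 and the schedule header: up to 24, with no lower bound.
- Both met: 22 to 24, which is 2 of the 4 hours.
- A 25 h sample passes section 8.4 and is late under 4.1.2. A 15 h sample does the reverse.

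**3. Half-life (assumption).** The documents give no oral half-life. Protocol section 4.2.1 equates a washout of 10-14 days with about 7-10 half-lives:
- 10 × 24 / 7 = 34.3 h and 14 × 24 / 10 = 33.6 h, so about 34 h.
- Pairing the ends the other way: 10 × 24 / 10 = 24 h and 14 × 24 / 7 = 48 h. This is used as the range.

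**4. Effect of sampling time.** Assuming mono-exponential decline, the difference from the 24 h value for a sample at t hours is 2^((24 − t)/half-life) − 1. For example, at t = 12 and 34 h: 2^(12/34) − 1 = +27.7%.

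| Hours since dose | Half-life 24 h | 34 h | 48 h |
|---|---|---|---|
| 12 | +41.4% | +27.7% | +18.9% |
| 16 | +26.0% | +17.7% | +12.2% |
| 22 | +5.9% | +4.2% | +2.9% |
| 26 | −5.6% | −4.0% | −2.8% |
| 36 | −29.3% | −21.7% | −15.9% |

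The 22-26 h limit keeps a sample within about 4% of the 24 h value (3% to 6% over the range). Without an hour limit, gaps of 12 h or 36 h give differences of roughly 16% to 41%.

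**The case against.** The strongest reply has four parts.

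- **The documents indicate which text governs PK.** Footnote 6 gives 22-26 h and sends the reader to section 8.4, the SAP footnote does the same, and 4.1.2 itself defers to the schedule. This stands in large part: the schedule as a whole does not contradict section 8.4; only its visit-window row does. But 4.1.2 names PK explicitly, so its limit cannot be set aside as a rule for other procedures.
- **The Day 14 window concerns the visit date.** Daily dosing continues, so moving the visit by a day does not itself change the time since dose. Day 1 dosing is with breakfast and Day 2 dosing follows the 24 h sample, which sets a morning pattern. This also stands. A 36 h gap needs a marked shift in dosing time or a missed dose. A 12 h gap needs less: someone who settles on a regular evening dose follows the counselling and could still attend a morning visit.
- **Little depends on Day 14.** It feeds no parameter in SAP Table 7, and the population PK model can use actual times. That is correct and limits the consequence.
- **The half-life is not drug-specific.** It comes from a washout remark and is applied to both drugs. That is why a range is shown and the percentages are illustrative only.

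A reader might also infer that the 22-26 h window lets a non-trough sample through on Day 29. It does not: it is 24 ± 2 h. Only the up-to-24-hours wording, with no lower bound, would admit one.

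**Conclusion.** Two points hold. An in-window Day 14 sample need not be a trough, because no hours-since-dose limit applies to it, while the other end-of-interval samples are held to 24 ± 2 h. And Day 29 PK timing is stated inconsistently, with agreement only at 22-24 h.

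The size is modest. For a mistimed Day 14 sample the illustrative difference is about +28% at 12 h (+19% to +41%) and −22% at 36 h (−16% to −29%), given mono-exponential decline and the implied half-life. These are possible cases, not expected average effects.

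Two stronger conclusions are not supported. One is that a comparison of Day 14 with Day 29 would be confounded by sampling time: neither document plans that comparison. The other is that the main results are at risk: every primary endpoint comes from the injection-phase profile. What is exposed is the descriptive lead-in concentration summaries, Day 29 Cτ and deviation review under SAP 8.3. Severity: minor.

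**What to change.** 1. In section 8.4, keep the Day 14 visit at ±1 day and add that the sample is pre-dose and drawn 22-26 h after the previous dose, the limit already used for Day 29.
2. Reconcile the Day 29 PK timing in section 4.1.2 and in the visit-window rows of the protocol and SAP schedules with footnote 6 and section 8.4, so that a single window decides PK deviations and review under SAP 8.3.

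The cost is wording in section 8.4, section 4.1.2 and two schedule headers. No visit or blood draw is added. The dose before the Day 14 visit (normally Day 13) has to be timed to the appointment, as section 8.4 already requires in effect for Day 28, and a few more samples may be flagged as out of window.
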